9.6.2 Statistical Methods for Safety Analyses

The APaT population will be employed for safety analyses. Safety analyses will be presented by Stage, and within Stage, Postdose 1, Postdose 2, and Postdose 1 or 2. All participants vaccinated and who have safety follow-up data will be included in the analysis of safety. Clinical AEs for 42 days following each of the study vaccination and the number and proportion of participants with the following clinical AEs will be tabulated as follows:

- Solicited injection-site reactions (redness, swelling, and pain/tenderness) of any intensity or size from Days 1 through 5 postvaccination for children and from Days 1 through 5 postdose 1 and 2 for adolescents/adults.
- Unsolicited injection-site AEs, regardless of severity or causality, from Day 1 through Day 42 postvaccination for children and from Days 1 through 42 postdose 1 and 2 for adolescents/adults.
- Maximum reported temperature ≥39.0°C oral equivalent from Day 1 through Day 28
 postvaccination for children and from Days 1 through 28 postdose 1 and 2 for
 adolescents/adults.

PRODUCT: V210
PROTOCOL/AMENDMENT NO.: 058-05

- Varicella- and herpes zoster-like rashes occurring from Day 1 through Day 42 postvaccination for children and from Days 1 through 42 postdose 1 and 2 for adolescents/adults.
- Systemic AEs from Day 1 through Day 42 postvaccination for children and from Days 1 through 42 postdose 1 and 2 for adolescents/adults.
- SAEs from Day 1 through Day 42 postvaccination for children and from Days 1 through 42 postdose 1 and 2 for adolescents/adults.
- Vaccine-related SAEs and death from Day 1 through the end of the study (Day 42 following the last vaccination).

Unless otherwise stated, all AEs will be collected for 42 days postvaccination after each dose of VARIVAXTM.

In addition, all CBC, blood chemistry and urinalysis data collected at Visit 1 and 3 days postvaccination for participants 7 years of age and older, will be summarized at all time points that these laboratory data are collected. However, no formal statistical testing will be conducted.

9.6.3 Summaries of Baseline Characteristics, Demographics, and Other Analyses

Participant characteristics of age, gender, and race/ethnicity will be summarized for all participants who enter the study. In addition, baseline serostatus for VZV will be presented.

The number (%) of participants with specific prior medications (incidence rate >0%) within 14 days prior to the vaccination will be summarized.

The number (%) of participants with specific concomitant medications (incidence rate >0%) within 42 days following each vaccination will be summarized.

A detailed participant accounting will be provided. This accounting will describe the number of participants allocated at study start, the number vaccinated at the vaccination visit, and the number of discontinuations and withdrawals during the safety follow-up period. This participant accounting will also indicate the number of participants who completed the study.

No other analyses are planned for this study.

9.7 Interim Analyses

No interim analyses are planned for this study.

9.8 Multiplicity

No multiplicity adjustment is required for this study.

9.9 Sample Size and Power Calculations

9.9.1 Sample Size and Power for Immunogenicity Analyses

Since this is an estimation study, no formal power calculation for immunogenicity was performed to determine the current sample size. However, the expected precision of estimation is given below. For immunogenicity summaries, the response rates and the associated 95% CI under different sample sizes of the adult, adolescents and children PP populations are estimated and presented in Table 7. In addition, the expected precision of the GMTs under different sample sizes of the adult and adolescents and children PP populations is presented in Table 8.

Table 7 Response Rates and Associated 95% CI Based on Different Sample Sizes of Per-Protocol Population

			95% Confidence Interval	
Population	Sample Size of Per-Protocol Population	Hypothetical Response Rate	Lower	Upper
Adult	40	0.80	0.64	0.91
Adult	40	0.85	0.70	0.94
		0.90	0.76	0.97
	45	0.80	0.65	0.90
		0.84	0.71	0.94
		0.91	0.79	0.98
Adolescent	25	0.80	0.59	0.93
		0.84	0.64	0.95
		0.92	0.74	0.99
	30	0.80	0.61	0.92
		0.83	0.65	0.94
		0.90	0.73	0.98
Children	55	0.80	0.67	0.90
		0.85	0.74	0.94
		0.91	0.80	0.97
	60	0.80	0.68	0.89
		0.85	0.73	0.93
		0.90	0.79	0.96

Confidential

Table 8 Expected Precision of GMTs under Different Sample Sizes of Per-Protocol Population

			95% Confidence Interval	
Population	Sample Size of Per-Protocol Population	Hypothetical GMT	Lower	Upper
Adult	40	80.0	58.1	110.1
(Postdose 2)		100.0	72.6	137.7
		120.0	87.2	165.2
	45	80.0	59.2	108.0
		100.0	74.0	135.0
		120.0	88.9	162.1
Adolescent	25	80.0	52.9	120.9
(Postdose 2)		100.0	66.2	151.1
		120.0	79.4	181.3
	30	80.0	55.1	116.2
		100.0	68.8	145.3
		120.0	82.6	174.3
Children	55	10.0	7.6	13.1
(Postvaccination)		12.0	9.2	15.7
		14.0	10.7	18.3
	60	10.0	7.7	12.9
		12.0	9.3	15.5
		14.0	10.8	18.1
Based on an assumed st	andard deviation of the 1	.0 for the log antibody	titers.	

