9.4 Analysis Endpoints

9.4.1 Immunogenicity Endpoints

The immunogenicity endpoints for VZV are:

- The response rates (defined as the percentage of participants with VZV antibody titer ≥5 gpELISA units/mL) 6 weeks postvaccination [for children] or 6 weeks postdose 2 [for adolescents/adults] among participants who are seronegative to VZV at baseline (titer <1.25 gpELISA units/mL).
- GMTs of VZV antibody as measured by gpELISA.
- The seroconversion rates (defined as the percentage of participants with VZV antibody titer ≥1.25 gpELISA units/mL) 6 weeks postvaccination [for children] or 6 weeks postdose 2 [for adolescents/adults] among participants who are seronegative to VZV at baseline (titer <1.25 gpELISA units/mL).

18-APR-2019

PRODUCT: V210
PROTOCOL/AMENDMENT NO.: 058-05

• For participants who are seropositive at baseline (baseline VZV antibody titer ≥1.25 gpELISA units/mL), the GMFR from Day 1 and the percentage of participants with ≥4-fold rise in antibody titer from Day 1 will be summarized at Day 1 and 6 weeks postvaccination for children and 6 weeks postdose 2 for adolescents/adults.

Immunogenicity summaries will be provided at Day 1 for all participants, at 6 weeks following vaccination for children, and at 6 weeks postdose 2 for adolescents and adults separately.

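### Do the adult and adolescent response rates in Table 7 contradict the GMTs in Table 8, and does anything follow from it?

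*Combined protocol and SAP*

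**What the plan says.** Section 9.9.1 describes an estimation study whose sample size was not derived from a power calculation, and then offers two tables of expected precision. For Table 7, "the response rates and the associated 95% CI under different sample sizes of the adult, adolescents and children PP populations are estimated". For GMTs, "the expected precision of the GMTs under different sample sizes of the adult and adolescents and children PP populations is presented in Table 8". Both tables use the same per-protocol sizes: adults 40 and 45, adolescents 25 and 30, children 55 and 60.

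- Table 7 takes response rates of 0.80, 0.85 and 0.90 (adults, n=40); 0.80, 0.84 and 0.91 (adults, n=45); 0.80, 0.84 and 0.92 (adolescents, n=25); 0.80, 0.83 and 0.90 (adolescents, n=30); and 0.80 to 0.91 for children.
- Table 8 takes GMTs of 80, 100 and 120 for adults and adolescents and 10, 12 and 14 for children, with a single log SD of 1.0. The log base is not given.

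The input column of each table is headed as hypothetical, and no row of one is matched to a row of the other. Section 9.4.1 gives the response endpoint as "defined as the percentage of participants with VZV antibody titer ≥5 gpELISA units/mL" among participants seronegative at baseline. Section 3 places the post-vaccination GMT in the same participants, and Section 9.5.1 restricts the primary analysis to baseline titers below 1.25.

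**The concern.** The response rate is a feature of the very titers whose geometric mean Table 8 describes. Once a GMT and a log SD are assumed, the share of titers at or above 5 is no longer free. Table 8 gives adults and adolescents GMTs more than eight times the children's (80/10 = 8, 120/14 = 8.6) at the same SD, while Table 7 gives all three groups nearly the same response rates. Both cannot describe one population.

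If Table 7's lower rates were realistic, Table 8's GMT intervals would be too narrow. If Table 8 were realistic, Table 7 would describe adult and adolescent precision far poorer than the trial will deliver. The study is meant to bridge global data to the Russian population without a hypothesis test, so a reader may look to these tables for what the numbers enrolled can show.

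**Working it through.** **Inputs.** Threshold 5 (Section 9.4.1); GMTs and log SD 1.0 (Table 8); response rates and sample sizes (Table 7); t-based GMT intervals and exact binomial intervals (Section 9.6.1).

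**Step 1: reproduce Table 8.** Limits are GMT × exp(±t(0.975, n−1) × 1.0/√n). For n=40, t = 2.0227 and √40 = 6.3246, so the half-width is 0.3198 and the factor is exp(0.3198) = 1.3769. GMT 80 gives 80/1.3769 = 58.1 and 80 × 1.3769 = 110.1, as printed. All 18 intervals reproduce to rounding. An SD of 1.0 on the log10 scale would give 38.3 to 167.1, so the table uses natural logs.

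**Step 2: reproduce Table 7.** For 32/40 the exact interval is 0.6435 to 0.9095, printed as 0.64 to 0.91. Seventeen of 18 rows reproduce. The exception is children, n=55, rate 0.85 (47/55), where the lower limit is 0.733 and 0.74 is printed. It plays no part in this point.

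**Step 3: response rate implied by Table 8.** Let k = ln(GMT/5), the distance in SDs from the threshold to the mean log titer. If titers are log-normal, the response rate is Φ(k). For any distribution with that mean and SD, the one-sided Chebyshev (Cantelli) inequality gives a rate of at least 1 − 1/(1 + k²). For GMT 80, k = ln 16 = 2.7726 and 1 − 1/8.687 = 0.885.

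| GMT | k | Log-normal rate | Minimum, any distribution |
|---|---|---|---|
| 80 | 2.773 | 0.997 | 0.885 |
| 100 | 2.996 | 0.999 | 0.900 |
| 120 | 3.178 | 0.999 | 0.910 |
| 10 | 0.693 | 0.756 | 0.32 |
| 12 | 0.876 | 0.809 | 0.43 |
| 14 | 1.030 | 0.848 | 0.51 |

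**Step 4: compare with Table 7.**

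- Adult and adolescent rates of 0.80, 0.83, 0.84 and 0.85 lie below 0.885, so they are excluded at every adult and adolescent GMT in Table 8. They fill 8 of the 12 rows.
- Rates of 0.90 to 0.92 are not excluded at GMT 80, although they are well below the log-normal 0.997.
- The children's rows do not conflict. The log-normal rates at GMT 12 and 14 match 0.80 to 0.85. Rates of 0.90 to 0.91 exceed the log-normal range but are far above the general minimum.

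**Step 5: size of the discrepancy, n=40.**

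- *Keep response 0.80 and GMT 80.* The smallest possible log SD is k√((1−p)/p) = 2.7726 × √(0.20/0.80) = 1.39. The half-width is 0.3198 × 1.386 = 0.443, and the interval is 51.4 to 124.6, against 58.1 to 110.1. At response 0.85 the minimum SD is 1.165 and the interval 55.1 to 116.1. If titers are also assumed log-normal, response 0.80 needs an SD of 2.7726/0.8416 = 3.29 and the interval is 27.9 to 229.4.
- *Keep GMT 80 and SD 1.0.* With log-normal titers nearly everyone responds. The exact interval is 0.91 to 1.00 for 40/40 and 0.87 to 1.00 for 39/40, against Table 7 lower limits of 0.64 to 0.76.

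**The case for a change.** The best case for a change is that the contradiction is proved from the plan's own figures. Calling the inputs hypothetical does not remove it, because no pairing of the 0.80 to 0.85 rows with an adult or adolescent GMT is possible. These are also the only figures given for immunogenicity precision, and restating two tables costs little.

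The incompatibility stands. The consequences claimed for it do not:

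- The tables did not produce the sample size. They describe precision at sizes already chosen, and the section says so.
- Neither table is miscalculated on this point. Each interval answers its own what-if question. A planner who shows a cautious range of response rates, where exact intervals are wider than they are near 1.00, and separately a range of GMTs, has not promised that the scenarios occur together.
- The dramatic interval of 27.9 to 229.4 needs a log-normal model that the plan does not state. What is proved without it is 51.4 to 124.6.
- In the other direction the error is conservative: the trial would estimate response more precisely than Table 7 suggests.
- The documents do not show which table's inputs are the realistic ones, so a correction would mean choosing between them without evidence.

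**Conclusion.** The mismatch is real but confined to planning illustrations. Table 7's adult and adolescent rates of 0.80 to 0.85 cannot hold together with Table 8's GMTs of 80 to 120 at SD 1.0. That rests on the SD being on the natural-log scale, which the reproduction of Table 8 confirms, and on both endpoints using the same seronegative per-protocol participants. It needs no assumption about the shape of the titer distribution. It does not extend to the children's rows, nor strictly to rates of 0.90 to 0.92 at GMT 80.

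No change is needed because nothing in the trial depends on the two tables agreeing. Sections 9.3 and 9.8 provide for no hypothesis and no multiplicity adjustment, and there is no success threshold. The reported intervals will be computed from observed titers by the methods in Section 9.6.1 and Table 6. Making the scenarios compatible would alter no enrolment target, analysis, reported result or conclusion. A reader who wants joint planning values can derive the response rate implied by any GMT and SD as in step 3.

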9.9.2 Sample Size and Power for Safety Analyses

The probability of observing at least 1 SAE in this study depends on the number of participants vaccinated and the underlying incidence of participants with an SAE in the study population. In Stage 1, it is expected that approximately 50 participants will contribute to the analysis of safety Postdose 1. In Stage 2, it is expected approximately 100 participants will contribute to the analysis of safety Postdose 1.

If no serious vaccine-related AEs are observed in this study in Stage 1 with 50 participants evaluable for safety, there will be a 97.5% probability that the true incidence rate is no more than 7.1%. If no serious vaccine-related AEs are observed in this study in Stage 2 with 100 children/adolescents in this study evaluable for safety, there will be a 97.5% probability that the true incidence rate is no more than 3.6%. The estimate of and the upper bound of the 95% CI for the underlying percentage of participants with a serious vaccine-related AEs given various hypothetical observed number of participants with a serious vaccine-related AEs among approximately 50 adult and approximately 100 adolescents/children are provided in Table 9.

V210-058-05 FINAL PROTOCOL 18-APR-2019

Table 9 Estimate of Incidence of Vaccine-Related Serious Adverse Events and Upper Bound of 95% Confidence Interval Based on Hypothetical Number of Participants with Vaccine-Related Serious Adverse Events

Population	Sample Size	Hypothetical Number of Participants With VR-SAE	Estimate of Incidence	Upper Bound of 95% Confidence Interval †
Adult	50	0	0.0%	7.1%
		1	2.0%	10.7%
		2	4.0%	13.7%
Adolescent/children	100	0	0.0%	3.6%
		1	1.0%	5.4%
		2	2.0%	7.0%

[†] Based on the two-tailed exact CI of a binomial proportion given in Collett [Collett, D. 1999].

9.10 Subgroup Analyses

For participants enrolled in the Stage 2 portion of the study, a summary of immunogenicity and safety endpoints will be provided based on following variables:

- Age: 12 months to 6 years, 7 to 12 years, and 13 to 17 years of age
- Dosing schedule:
 - o participants receiving 1 dose of VARIVAXTM (12 months to 12 years of age)
 - o participants receiving 2 doses of VARIVAXTM (13 to 17 years of age)

9.11 Compliance (Medication Adherence)

The number and proportion of allocated participants receiving each vaccination will be summarized (Section 9.12).

9.12 Extent of Exposure

The extent of exposure will be summarized by the number and proportion of allocated participants administered VARIVAXTM at each scheduled vaccination.

VR-SAE = vaccine-related serious adverse event

PRODUCT: V210
PROTOCOL/AMENDMENT NO.: 058-05

10 SUPPORTING DOCUMENTATION AND OPERATIONAL CONSIDERATIONS

10.1 Appendix 1: Regulatory, Ethical, and Study Oversight Considerations

10.1.1 Code of Conduct for Clinical Trials

Merck Sharp and Dohme Corp., a subsidiary of Merck & Co., Inc. (MSD)

Code of Conduct for Interventional Clinical Trials

I. Introduction

A. Purpose

MSD, through its subsidiaries, conducts clinical trials worldwide to evaluate the safety and effectiveness of our products. As such, we are committed to designing, implementing, conducting, analyzing and reporting these trials in compliance with the highest ethical and scientific standards. Protection of participants in clinical trials is the overriding concern in the design of clinical trials. In all cases, MSD clinical trials will be conducted in compliance with local and/or national regulations (eg, International Council for Harmonisation Good Clinical Practice [ICH-GCP]) and in accordance with the ethical principles that have their origin in the Declaration of Helsinki.

B. Scope

Highest ethical and scientific standards shall be endorsed for all clinical interventional investigations sponsored by MSD irrespective of the party (parties) employed for their execution (eg, contract research organizations, collaborative research efforts). This Code is not intended to apply to trials that are observational in nature, or which are retrospective. Further, this Code does not apply to investigator-initiated trials, which are not under the full control of MSD.

II. Scientific Issues

A. Trial Conduct

1. Trial Design

Except for pilot or estimation trials, clinical trial protocols will be hypothesis-driven to assess safety, efficacy, and/or pharmacokinetic or pharmacodynamic indices of MSD or comparator products. Alternatively, MSD may conduct outcomes research trials, trials to assess or validate various endpoint measures, or trials to determine patient preferences, etc.

The design (ie, participant population, duration, statistical power) must be adequate to address the specific purpose of the trial. Participants must meet protocol entry criteria to be enrolled in the trial.

2. Site Selection

MSD selects investigative sites based on medical expertise, access to appropriate participants, adequacy of facilities and staff, previous performance in clinical trials, as well as budgetary considerations. Prior to trial initiation, sites are evaluated by MSD personnel to assess the ability to successfully conduct the trial.

3. Site Monitoring/Scientific Integrity

Investigative trial sites are monitored to assess compliance with the trial protocol and general principles of Good Clinical Practice (GCP). MSD reviews clinical data for accuracy, completeness, and consistency. Data are verified versus source documentation according to standard operating procedures. Per MSD policies and procedures, if fraud, scientific/research misconduct, or serious GCP-noncompliance is suspected, the issues

PRODUCT: V210

PROTOCOL/AMENDMENT NO.: 058-05

are investigated. When necessary, the clinical site will be closed, the responsible regulatory authorities and ethics review committees notified.

B. Publication and Authorship

Regardless of trial outcome, MSD commits to publish primary and secondary results of its registered trials of marketed products in which treatment is assigned, according to the prespecified plans for data analysis. To the extent scientifically appropriate, MSD seeks to publish the results of other analyses it conducts that are important to patients, physicians, and payers. Some early phase or pilot trials are intended to be hypothesis-generating rather than hypothesis testing, in such cases, publication of results may not be appropriate since the trial may be underpowered and the analyses complicated by statistical issues such as multiplicity.

MSD's policy on authorship is consistent with the recommendations published by the International Committee of Medical Journal Editors (ICMJE). In summary, authorship should reflect significant contribution to the design and conduct of the trial, performance or interpretation of the analysis, and/or writing of the manuscript. All named authors must be able to defend the trial results and conclusions. MSD funding of a trial will be acknowledged in publications.

III. Participant Protection

A. Ethics Committee Review (Institutional Review Board [IRB]/Independent Ethics Committee [IEC])

All clinical trials will be reviewed and approved by an IRB/IEC before being initiated at each site. Significant changes or revisions to the protocol will be approved by the ethics committee prior to implementation, except changes required urgently to protect participant safety that may be enacted in anticipation of ethics committee approval. For each site, the ethics committee and MSD will approve the participant informed consent form.

B. Safety

The guiding principle in decision-making in clinical trials is that participant welfare is of primary importance. Potential participants will be informed of the risks and benefits of, as well as alternatives to, trial participation. At a minimum, trial designs will take into account the local standard of care.

All participation in MSD clinical trials is voluntary. Participants enter the trial only after informed consent is obtained. Participants may withdraw from an MSD trial at any time, without any influence on their access to, or receipt of, medical care that may otherwise be available to them.

C. Confidentiality

MSD is committed to safeguarding participant confidentiality, to the greatest extent possible. Unless required by law, only the investigator, Sponsor (or representative), ethics committee, and/or regulatory authorities will have access to confidential medical records that might identify the participant by name.

D. Genomic Research

Genomic research will only be conducted in accordance with a protocol and informed consent authorized by an ethics committee.

IV. Financial Considerations

V210-058-05 FINAL PROTOCOL

A. Payments to Investigators

Clinical trials are time- and labor-intensive. It is MSD's policy to compensate investigators (or the sponsoring institution) in a fair manner for the work performed in support of MSD trials. MSD does not pay incentives to enroll participants in its trials. However, when enrollment is particularly challenging, additional payments may be made to compensate for the time spent in extra recruiting efforts.

Confidential

PRODUCT: V210
PROTOCOL/AMENDMENT NO.: 058-05

MSD does not pay for participant referrals. However, MSD may compensate referring physicians for time spent on chart review to identify potentially eligible participants.

B. Clinical Research Funding

Informed consent forms will disclose that the trial is sponsored by MSD and that the investigator or sponsoring institution is being paid or provided a grant for performing the trial. However, the local ethics committee may wish to alter the wording of the disclosure statement to be consistent with financial practices at that institution. As noted above, all publications resulting from MSD trials will indicate MSD as a source of funding.

C. Funding for Travel and Other Requests

Funding of travel by investigators and support staff (eg, to scientific meetings, investigator meetings, etc.) will be consistent with local guidelines and practices.

V. Investigator Commitment

Investigators will be expected to review MSD's Code of Conduct as an appendix to the trial protocol, and in signing the protocol, agree to support these ethical and scientific standards.

